#### 4.5 fNIRS Data Analysis

The fNIRS data will undergo preprocessing (performed in MATLAB) including filtering (to remove noise and drift), motion artifact correction, and segmentation of the task period. For each participant and each session (baseline, 3m, 6m), we will derive summary metrics such as the average oxyhemoglobin concentration change ( $\Delta[\text{HbO}_2]$ ) in specific regions of interest during the cognitive task relative to rest baseline. We might average signals over channels covering the left orbitofrontal cortex (OFC), right OFC, ventrolateral PFC, etc., based on the sensor layout. These ROI-level  $\Delta\text{HbO}_2$  will be the variables used for analysis.

**Longitudinal ROI Analysis:** Using GEE, we will model  $\Delta\text{HbO}_2$  as the outcome with group, time (0, 3, 6 months), and group $\times$ time as factors, similar to other outcomes. We anticipate, for instance, a significant group $\times$ time effect in left OFC  $\text{HbO}_2$ , indicating the intervention group's  $\text{HbO}_2$  increases over time relative to control (as observed in preliminary analyses). If GEE shows significance, we will follow up with post-hoc tests of group differences at 3 and 6 months, and time differences within each group. If data are normally distributed and complete, an LMM could also be used for confirmation. If some fNIRS measurements are missing (due to technical issues or dropouts), GEE can handle missing under MAR assumptions.

**Correlation with Clinical Outcomes:** We will compute Pearson or Spearman correlations between changes in fNIRS metrics (e.g.,  $\Delta\text{HbO}_2$  from baseline to 6m in a region) and changes in clinical scores (e.g., PHQ-9 drop) across individuals. A positive correlation would indicate that participants with larger brain activation increases tended to have greater depression improvement, supporting fNIRS as a biomarker. A small p-value would suggest significance of this correlation.

**ROC Analysis:** One key exploratory analysis is to evaluate whether fNIRS measures can classify depression status. We will define a binary variable for depression at 6 months (for

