example, PHQ-9  $\geq 10$  indicating clinically significant depressive symptoms vs  $< 10$  indicating minimal symptoms). We will then take certain fNIRS measures (like the 6-month left OFC HbO2 level or the change in that level from baseline) and perform ROC curve analysis. The area under the ROC curve (AUC) will be calculated to assess discrimination ability. If AUC is significantly above 0.5, it indicates some predictive value. We will identify the optimal cutoff on the fNIRS measure that maximizes Youden's J (sensitivity + specificity - 1). For that cutoff, we will report sensitivity, specificity, positive predictive value, and negative predictive value. To account for sample variability, we will use a bootstrap approach (e.g., 1000 bootstrap samples of the data) to derive a confidence interval for the AUC and for the sensitivity/specificity at the chosen cutoff. For example, in preliminary findings, a cutoff  $\Delta$ HbO2 of approximately -0.47 mmol·mm in left OFC was identified for the experimental group depression prediction; we will verify if similar thresholds emerge and their stability via bootstrapping. This analysis is exploratory and aimed at generating hypotheses for future larger studies on using fNIRS as a screening tool.

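### SAP 4.5 chooses the fNIRS cut-off by maximising Youden's J and reports accuracy there in the same data, with no correction for selection optimism

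*SAP*

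**What the plan says.** The plan is in SAP Section 4.5, ROC Analysis.

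- **Selection.** "We will identify the optimal cutoff on the fNIRS measure that maximizes" Youden's J, that is, sensitivity + specificity - 1. Sensitivity, specificity, PPV and NPV are reported at that cut-off.
- **Bootstrap.** About 1000 resamples of the trial data serve to "derive a confidence interval for the AUC and for the sensitivity/specificity at the chosen cutoff". No split sample, cross-validation, external validation or optimism correction appears in either document.
- **Earlier cut-off.** A left orbitofrontal value of about -0.47 mmol·mm "was identified for the experimental group depression prediction; we will verify if similar thresholds emerge and their stability via bootstrapping". No dataset, sample size or reference is given. The longitudinal part of the same section mentions a group-by-time effect "as observed in preliminary analyses", also without a source.
- **Predictor.** The examples are the 6-month left orbitofrontal "level or the change in that level from baseline".
- **Class to be predicted.** Section 4.5 offers, as an example, PHQ-9 of 10 or more, "indicating clinically significant depressive symptoms". SAP Section 3 (fNIRS biomarkers) refers back to a PHQ-9 threshold already noted. The only one noted before that point is below 5, the remission example under Depression Severity.
- **Status.** "This analysis is exploratory and aimed at generating hypotheses for future larger studies".

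**The concern.** A cut-off that maximises J in a sample fits that sample's chance features as well as the real signal. Accuracy measured at the maximum in the same patients is therefore too high on average. Bootstrapping at the fixed, already chosen cut-off describes sampling variability around the inflated value and leaves the inflation in place.

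The results are meant to inform later work on fNIRS as a screening tool, and the Protocol's hypotheses include predicting remission with reasonable accuracy. A later study designed around these figures would start from sensitivity and PPV that a new sample would not be expected to reproduce.

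Two smaller gaps bear on the same result. With the PHQ-9 threshold unsettled, patients scoring 5-9 change class. With the source of -0.47 unstated, a reader cannot tell whether finding a similar value in this trial is an independent check or a circular one.

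**Working it through.** **The plan's own figure.** The -0.47 cut-off cannot be reproduced, because neither data nor source is given. The size of the bias therefore has to come from simulation.

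**Inputs from the documents.** N = 92, or 46 per arm (Protocol, Sample Size); selection by maximum J; 1000 resamples (SAP 4.5).

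**Assumed, because the documents are silent.** 15-40% depressed at 6 months (14, 25 or 37 of 92; 7, 12 or 18 of 46). The marker is normal with equal SD in both classes and its direction is fixed. The main case is a true AUC of 0.75, with 0.5 as the null and 0.65-0.85 as the range.

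**Formulas.** The separation between classes is μ = √2 × Φ⁻¹(AUC). For AUC 0.75, μ = 1.414 × 0.674 = 0.954. The best attainable J is 2Φ(μ/2) - 1 = 2Φ(0.477) - 1 = 0.37. In each simulated dataset the cut-off is chosen by maximum J. Apparent accuracy is read from the sample, and true accuracy at the chosen cut-off from the normal distributions.

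**Results, n = 92**

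| Quantity | Apparent | True at chosen cut-off |
|---|---|---|
| J, AUC 0.5 | 0.12-0.17 | 0 |
| J, AUC 0.75 | 0.44-0.47 | 0.34 |
| Sensitivity, AUC 0.75 | 0.72-0.76 | 0.64-0.67 |
| PPV, AUC 0.75 | 0.36-0.65 | 0.30-0.60 |

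At AUC 0.75 the excess in J is 0.44 - 0.34 = 0.10 to 0.47 - 0.34 = 0.13. Specificity accounts for only about 0.03 of it, so most falls on sensitivity, which is estimated from the smaller class. The PPV excess is 0.65 - 0.60 = 0.05 to 0.36 - 0.30 = 0.06. Over AUC 0.65-0.85 the excess in J is 0.08-0.15. Losing patients to the planned 43 per arm (n = 86) changes little: with 30% depressed and AUC 0.7, the excess in J is 0.112 against 0.108 at n = 92.

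**What the planned bootstrap does.** With 30% depressed and a useless marker, mean apparent J is 0.136 and the mean over fixed-cut-off resamples is also 0.136, so none of the bias is removed. The 95% interval for J excludes 0 in about 26% of such datasets. At AUC 0.75 and n = 92, the 95% interval for sensitivity covers the truth in about 74-87% of datasets. It lies wholly above the truth in 14-21%, against 3-4% for a cut-off fixed in advance.

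**One arm only, n = 46, AUC 0.75.** Apparent J is 0.48-0.52 against a true 0.32-0.34, and apparent sensitivity 0.75-0.81 against 0.64-0.67.

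**What correction achieves, n = 92.** Optimism-corrected J is 0.04-0.06 at the null (truth 0) and 0.38 at AUC 0.75 (truth 0.34). Coverage for sensitivity rises from 74-87% to 83-93%. Re-selecting the cut-off in each resample without subtracting the optimism makes matters worse: with 30% depressed at the null, mean J becomes 0.18 instead of 0.136.

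**The case against.** The strongest reply is that the analysis is declared exploratory, fNIRS is not a primary endpoint, and the AUC is reported with its own interval. All of that stands. For one pre-named metric the AUC does not depend on the cut-off; its interval lies above 0.5 in only 3-4% of null datasets, so a useless marker would usually be recognised. But an exploratory label does not tell the reader that sensitivity and PPV are inflated, and those are the figures a screening study would carry forward.

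Four stronger readings are tempting, and the documents do not support them.

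- **That an unstable threshold would be declared stable.** The SAP asks only whether similar thresholds emerge. If cut-offs are re-derived in resamples, the check would itself show a wide spread: at AUC 0.75 about 58-63% of resamples give a cut-off within 0.25 SD of the one chosen. Measured from the population-optimal cut-off, agreement is 38-49%. Resampling is thus somewhat flattering, but it would not hide the instability.
- **That -0.47 came from this trial.** The reference to an experimental group makes this possible, and it would then sit awkwardly with SAP Section 1, which reports no interim analyses and a SAP final before the database was unlocked. The documents do not settle it. If the value is external, comparing it with this trial is a legitimate independent check.
- **That the n = 46 figures describe the plan.** Depression status is defined without restriction to an arm; only the preliminary cut-off is tied to one.
- **That the AUC is inflated by choosing the better of 6-month level and change.** The SAP does not say it will report only the better. Doing so would move the mean null AUC to just 0.52-0.54 at n = 92, assuming a baseline to 6-month correlation of 0.3-0.7.

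**Conclusion.** The concern holds for the accuracy figures at the selected cut-off. The direction of the bias follows from the method. Its size depends on the assumed depression rate, true AUC and normal marker. With n = 92, 15-40% depressed and AUC 0.75, sensitivity is overstated by roughly a tenth on the 0-1 scale or somewhat less, PPV by 0.05-0.06 and specificity by about 0.03, and the interval for sensitivity under-covers. The bias would be larger if the ROC were run in one arm. A reader might infer that the trial's main conclusions are at risk. They are not: no primary outcome, test or sample size is touched. The unsettled PHQ-9 class and the unsourced -0.47 are gaps in specification, not evidence of an undisclosed look at the data.

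**What to change.** 1. In each of the planned 1000 resamples, re-select the Youden cut-off, together with the metric, region of interest or PHQ-9 threshold if any of these is chosen from the data. Optimism is the accuracy in the resample minus the accuracy of the same cut-off in the original data. Subtract its mean from apparent sensitivity, specificity, PPV and NPV, and shift the interval limits by the same amounts.
2. Report apparent and corrected values side by side, with the bootstrap distribution of the cut-off. Describe this as internal validation only, and replace the wording about verifying the threshold.
3. State one PHQ-9 threshold for the ROC class and use it in both SAP Section 3 and Section 4.5.
4. State the source of the -0.47 cut-off. If it is this trial, label the value data-derived and reconcile it with SAP Section 1.

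The cost is a modified loop over resamples already planned and a few sentences, with no new data. Reported accuracy will look less favourable. The correction is only partial: at n = 46 and AUC 0.75, corrected J is 0.38-0.39 against a true 0.32-0.34. The interval shift helps little when very few patients are depressed; with 7 of 46, coverage for sensitivity moves only from about 61% to 65%.

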#### **4.6 Handling of Missing Data and Outliers**

As noted, the mixed models and GEE inherently handle missing longitudinal data under MAR. We will examine the extent of missingness at each follow-up. If  $> 10\%$  of data are missing for key outcomes, we will do multiple imputation as described (Section 4.3). We will also conduct a per-protocol analysis (excluding dropouts) for comparison. If ITT and PP results differ meaningfully, we will attempt to understand why (e.g., maybe dropouts in control differ in outcome).

**Outliers:** Before final analysis, data will be checked for any outlier values (e.g., a BI score that is impossible, or an extreme fNIRS value beyond physiological range). Any obvious data entry errors will be corrected (by checking source documents). Legitimate outliers will be kept in the analysis, but we may perform robustness checks by running analyses with and without outliers to see if results change. If a particular participant's data unduly influence a result (Cook's distance or residual diagnostics in regression), this will be reported.

For questionnaire scales, if an individual item is missing, we will handle per instrument guidelines (often prorating or mean substitution if  $\leq 1$  item missing on PHQ-9 or FSS, etc.), otherwise the score is set to missing.

#### **4.7 Assumption Checks**

**Normality and Homogeneity:** We will use Shapiro-Wilk tests and Q-Q plot inspections for normality of residuals for key models. If PHQ-9 or other scores show significant skew, we may confirm results with nonparametric tests (e.g., Wilcoxon rank-sum for endpoint differences, or a rank-based ANOVA). Similarly, Levene's test will be used to assess equality of variances between groups for t-test/ANOVA assumptions. The repeated measures ANOVA requires sphericity; we will apply Mauchly's test for sphericity. If sphericity is violated, the Greenhouse-Geisser correction will be applied to F-tests (as already anticipated). The linear mixed model approach does not require sphericity, which is one reason we favor it primarily.

**Independence:** Given randomization, independence of observations across participants is expected. We will ensure no clustering effects (since single center, no cluster-randomization, except repeated measures within subjects which is handled by paired models).

**Model Fit:** For mixed models, we will check that model residuals vs fitted plots show no major deviations (e.g., heteroscedasticity). If necessary, we might try a transformation of an outcome (e.g., log-transform FSS if very skewed). For binary outcomes (if any logistic regression is used in subgroup or supplementary analyses), we will check for small sample issues (Firth's correction if cell counts are small) and overfitting.

**Multiplicity:** We acknowledge multiple outcomes are being tested (four primary scales). Our focus is on the collective evidence across these outcomes rather than any single hypothesis. Thus, we are not formally adjusting  $\alpha$  for multiple comparisons in the primary domain; however, we will interpret the pattern of results (e.g., if all four move in the favorable direction with several significant, that strengthens conclusions). Secondary outcomes and subgroup analyses will be considered exploratory.

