- **6-Month Follow-up (Month 6, end of study):** At the end of the 6-month study period, all participants undergo the final evaluation. The same battery of outcome measures (PHQ-9, FSS, MMSE, Barthel Index, SIS) is administered, and the **final fNIRS** measurement is conducted. The 6-month outcomes represent the primary endpoint for evaluating intervention effectiveness. By this time, the intervention group has concluded all activities (the last home visit by the physical therapist typically occurs around month 5 or 6 with the monthly schedule). We document any post-study referrals or ongoing care plans for both groups. After completing the 6-month assessment, participants are thanked and exit the study. Those in the control group are offered an opportunity to receive the intervention program after study completion, if appropriate, as an ethical consideration.

Sample Size and Justification

The sample size was determined based on detecting a clinically meaningful difference in depression outcomes between the two groups at 6 months. Using a two-sample comparison of mean change in PHQ-9 scores (intervention vs control), we assumed a difference in mean PHQ-9 reduction of approximately 3.43 points with a standard deviation of about 5.5, based on prior research on post-stroke depression interventions [27]. With a two-sided $\alpha=0.05$ and power (1– β) of 0.80, the estimated minimum sample required was 43 patients per group (calculated via the formula for comparing two means). We planned to enroll 46 patients in each group (total N=92) to account for potential drop-outs and ensure adequate power. This sample size also offers >80% power to detect medium-to-large effects on secondary continuous outcomes like FSS and Barthel Index, given similar variance assumptions. The actual achieved sample size was 92, which meets these targets. No interim analyses for efficacy were planned (due to the relatively short intervention duration and moderate sample size), so the full sample contributes to the final analysis.

Randomization, Allocation Concealment, and Blinding

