## 4. Statistical Methods

### 4.1 General Analysis Principles

All statistical tests will be two-sided with a significance level of  $\alpha = 0.05$ . Outcomes will be analyzed primarily in the ITT population. We will use **descriptive statistics** to summarize baseline characteristics and outcomes at each time point by group. For continuous variables, we will report means and standard deviations (or medians and interquartile ranges if non-normal). Categorical variables will be summarized as counts and percentages. No formal hypothesis testing will be performed on baseline characteristics (any baseline differences observed will be noted but understood as chance differences due to randomization). Where relevant, 95% confidence intervals (CIs) will be provided for estimated effects (e.g., mean differences, odds ratios). All analyses will be conducted using Stata (v16.0) and R statistical software. fNIRS signal processing will utilize MATLAB with the NIRSIT toolbox, with processed outputs then analyzed in Stata/R.

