### 4.3 Primary Outcome Analysis

#### *Longitudinal Analysis (Main Approach):*

We will utilize **repeated measures analysis** to assess treatment effects on the continuous primary outcomes (PHQ-9, FSS, MMSE, BI) over time. A linear mixed-effects model (LMM) will be fitted for each outcome with fixed effects for treatment group (intervention vs control), time (categorical: baseline, 1m, 3m, 6m), and the group  $\times$  time interaction. Each model will include a random intercept for each participant to account for within-subject correlations over time (assuming an unstructured covariance or other appropriate structure based on model fit). The primary parameter of interest is the group  $\times$  time interaction term at 6 months, which tests whether the change from baseline to 6 months differs between groups. If this interaction is significant ( $p < 0.05$ ), it indicates a differential treatment effect over time. We will report the estimated mean change from baseline to 6 months in each group and the difference in change between groups (with 95% CI and p-value). For reference, we will also report group differences at intermediate time points (1 and 3 months) from the same model, though these are secondary.

Assumptions of the LMM (normality of residuals, etc.) will be checked. If necessary (e.g., for skewed distributions like FSS), we may apply transformations (e.g., log transform) or use a nonparametric approach. However, given our sample size, the LMM with robust standard errors should be adequate even if mild deviations exist.

As an alternative verification, we may perform a **GEE analysis** for each outcome. The GEE will treat time as a repeated factor and use an exchangeable working correlation to account for repeated measures. GEE provides population-averaged estimates and is robust to misspecification of correlation. The results from GEE (in terms of intervention effect over time) will be compared to the LMM results. We anticipate they should converge, but any discrepancies will be examined (e.g., if dropout patterns influence results differently).

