#### *Endpoint Analysis (Supportive):*

We will also analyze the **6-month endpoint directly** using analysis of covariance (ANCOVA) or t-tests. For each outcome, an ANCOVA will be conducted with the 6-month score as the dependent variable, treatment group as factor, and baseline score of that outcome as a covariate. This is a common approach to improve precision. The estimated group effect from ANCOVA (difference in 6-month mean outcomes adjusted for baseline) will be reported with 95% CI. Alternatively, we may compare the change scores (6-month minus baseline) between groups via an independent-samples t-test (equivalent to ANCOVA under equal baseline means). Both approaches yield the treatment effect estimate; ANCOVA is preferred if there were any baseline imbalances in that outcome.

Additionally, within-group changes from baseline will be assessed using paired t-tests for descriptive context (e.g., PHQ-9 reduction in intervention group, p-value; in control group, p-value). These within-group tests will not be used to infer treatment efficacy but to illustrate magnitude of change.

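### SAP 4.7 does not say which score its optional rank-sum check uses and names no baseline-adjusted rank test; a rank ANCOVA would use the baseline already collected

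*SAP*

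**What the plan says.** The primary analysis (SAP 4.3, Longitudinal Analysis) is a linear mixed model for each of PHQ-9, FSS, MMSE and Barthel Index. Its key parameter is the group-by-time term at 6 months, which "tests whether the change from baseline to 6 months differs between groups".

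The supportive analysis (SAP 4.3, Endpoint Analysis) begins: "We will also analyze the 6-month endpoint directly using analysis of covariance (ANCOVA) or t-tests". It describes an ANCOVA of the 6-month score with the baseline score as covariate and, as an alternative, a t-test on change scores.

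SAP 4.7 (Normality and Homogeneity) then says that, if scores show significant skew, "we may confirm results with nonparametric tests (e.g., Wilcoxon rank-sum for endpoint differences, or a rank-based ANOVA". SAP 4.3 also allows a nonparametric approach for skewed outcomes without naming one. The protocol's Schedule of Events has all four primary scales measured at baseline, before randomisation.

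**The concern.** A check for non-normality should differ from the analysis it checks in one respect only: its reliance on the shape of the distribution. A two-sample rank-sum test on 6-month scores differs in a second respect, because it has no baseline term. If it disagrees with the mixed model, the reader cannot tell whether skew or the discarded baseline is the cause. A chance baseline difference between arms also passes straight into the check.

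The text leaves open which score is ranked. The Endpoint Analysis section calls the 6-month score the endpoint and uses a separate term for the change score, so the 6-month reading is the more natural one. It is not the only one.

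**Working it through.** **Inputs.** From the protocol's Sample Size section: "Using a two-sample comparison of mean change in PHQ-9 scores (intervention vs control", with a "difference in mean PHQ-9 reduction of approximately 3.43 points with a standard deviation of about 5.5"; "the estimated minimum sample required was 43 patients per group"; "We planned to enroll 46 patients in each group (total N=92". SAP 4.1 sets two-sided testing at 0.05. Because the planning comparison is of changes, 5.5 is read as the SD of change. The baseline-to-6-month correlation (rho) is not in the documents, so it is assumed and varied.

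**1. The plan's own figure.** n per arm = 2 × [5.5 × (1.96 + 0.842) / 3.43]² = 40.4, so 41. The t-based version gives 42, and dividing 40.4 by the rank-sum efficiency 3/π gives 42.3, so 43. The stated 43 is reproduced closely enough for the inputs to be used.

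**2. Approximate power at 46 per arm, normal scores, equal SD at both visits.** The SD of a single score is 5.5 / √(2(1 − rho)), which is 4.65, 5.50 and 7.10 at rho 0.3, 0.5 and 0.7.

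- Rank-sum on the 6-month score: Φ(3.43 / [SD × √(2 / (46 × 3/π))] − 1.96). At rho 0.7: 3.43 / (7.10 × 0.2134) − 1.96 = 0.30, or 62%. At rho 0.5 it is 83%, and at 0.3 it is 93%.
- Baseline-adjusted comparison (parametric ANCOVA): replace SD by SD × √(1 − rho²) and use n = 46. This gives 96%, 93% and 90% at rho 0.3, 0.5 and 0.7.
- t-test on change: 3.43 / (5.5 × √(2/46)) − 1.96 = 1.03, or 85% at every rho.

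**3. Simulated power, rank-sum on the 6-month score versus rank ANCOVA** (46 per arm, SD of change 5.5):

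| rho | Skewed: rank-sum | Skewed: rank ANCOVA | Normal: rank-sum | Normal: rank ANCOVA |
|---|---|---|---|---|
| 0.3 | 98% | 98% | 91% | 94% |
| 0.5 | 92% | 97% | 82% | 92% |
| 0.7 | 77% | 95% | 60% | 86% |

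The skewed columns matter more, because skew is what triggers the check. Repeat simulations agree to within about 2 points, and both rank tests reject in about 5% of trials under the null.

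**4. How often the check fails to confirm.** The t-test on change stands in for the primary contrast. Under normal scores it is significant while the 6-month rank-sum test is not in about 11% of trials at rho 0.5 and 30% at rho 0.7. For rank ANCOVA the corresponding figures are about 2.5% and 5%. The normal case contains no skew, so the excess comes from dropping baseline. Under gamma-skewed scores (shape 2) the rank-sum figures are 1%, 4% and 15% at rho 0.3, 0.5 and 0.7.

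**5. If the rank-sum test is run on change scores.** Under normal scores, power against rank ANCOVA is 83% vs 94% at rho 0.3, 82% vs 91% at 0.5, 82% vs 85% at 0.7, and equal at 0.8. It fails to confirm a significant change-score t-test in only about 3% of trials. Under skew the ordering at high rho depends on how the skew is generated. One model at 43 per arm gave 87% vs 95% at rho 0.7; another put rank-sum on change 2 to 4 points ahead at rho 0.7 to 0.8.

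**6. If 5.5 is the SD of the 6-month score instead** (43 per arm, rho 0.3, 0.5, 0.7). Normal: 80% vs 83%, 81% vs 90%, 80% vs 97%. Skewed: 92% vs 94%, 92% vs 96%, 91% vs 99%. Rank ANCOVA still leads throughout.

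**The case against.** The strongest reply is that SAP 4.7 commits to very little. The check is optional, the rank-sum test is one of two examples, and the other, a rank-based ANOVA, could carry baseline as one of the repeated visits. The rank-sum test could also be meant for change scores, since it is the natural counterpart of the change-score t-test in the Endpoint Analysis section. On that reading baseline is used and most of the disagreement disappears. All of this stands. It is why the point is about an unspecified score and a missing method, not about a wrong test having been chosen.

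Second, the large losses need a high rho, and the documents give none. At rho 0.3 there is little or nothing to gain over the 6-month rank-sum test. Under skew at rho 0.3 and 0.5 that test even has more power than the change-score t-test (98% and 93% against 85% and 84% in one run). This also stands, and limits the size of the point.

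Third, baseline is already used in the mixed model and the ANCOVA, and SAP 4.3 offers transformation, robust standard errors and GEE. That is correct, and it keeps the point minor.

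Fourth, Quade's method does not test change either. True, but it conditions on baseline as the SAP's own ANCOVA does, which is what the 6-month rank-sum test lacks.

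A reader might infer that the SAP makes an unadjusted 6-month rank-sum test the check that decides whether the primary result is confirmed, so that real effects would be reported as unconfirmed. The documents do not support this: no rule lets the check overrule the mixed model, and nothing says how a disagreement would be reported.

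**Conclusion.** The point holds as a minor improvement. SAP 4.7 leaves the ranked score unspecified, and the SAP names no rank method that adjusts for baseline. On the 6-month reading, the check discards information the trial already has. Under skew the cost is nil at rho 0.3, about 5 points of power at 0.5 and 18 points at 0.7; under normal scores it is about 3, 10 and 26 points. On the change-score reading with normal scores, the cost is about 11 points at rho 0.3, 9 at 0.5 and 3 at 0.7.

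These figures assume a location shift of 3.43, an SD of change of 5.5, 46 per arm with no dropout, and an assumed rho. They are derived for PHQ-9; the documents give no planning values for the other three scales. In none of the settings run did the 6-month rank-sum test clearly beat rank ANCOVA. The primary analysis is not affected.

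**What to change.** In SAP 4.7, replace the unadjusted rank-sum example with Quade's rank ANCOVA for PHQ-9, FSS, MMSE and Barthel Index. Rank the 6-month scores and the baseline scores over both arms together, regress the 6-month ranks on the baseline ranks, and compare the residuals between arms. If the rank-based ANOVA is kept as an option, say which visits enter it. State that the check is a sensitivity analysis, that the mixed model remains primary, and how a disagreement will be described.

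The cost is a sentence or two in the SAP and a few lines of Stata or R, with no new data. The small downside is that rank ANCOVA gives a p-value without an estimate in scale points, as does the test it replaces.
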